8.7.7 Imaging: X-ray and CT scan (Surgery)

The presence of electrode tip fold-over may be detected intra-operatively via modified Stenver's view X-ray, so that it may be corrected in-situ by removal and re-insertion of the electrode array. If the folding persists the back-up device should be employed. The correct positioning of the electrode within the scala will be assessed by post-operative cone beam CT scan. The resultant scan will be assessed post-operatively by the surgical team.

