Residual risks for the investigational device compared to a similar device, such as the Nucleus CI512, relate to use errors which may increase the risk of tip fold-over. It should be noted that tip folding is not unknown in similar pre-curved arrays or in straight arrays. The presence of a tip fold-over does not usually produce any clinical symptoms or adverse effect. However it is likely that the distribution of current produced by the electrode array would be perturbed such that performance outcomes could be limited (such as speech recognition scores).

All residual risks for the investigational device will be described in the Patient Informed Consent (PIC)

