7 RISKS AND ANTICIPATED DEVICE EFFECTS

For this clinical investigation, safety will be defined as freedom from device or procedure-related adverse events. The risks and anticipated adverse device effects that are to be collected in the clinical investigation are:

1. The number and percentage of subjects with electrode tip fold-overs as determined by X-ray. It is not intended that this data serve as a measure of treatment success since the focus of this study is hearing benefit.
2. The number and percentage of subjects with electrode not fully within the scala tympani as determined by cone beam CT scan
3. The number and percentage of subject with complete loss of hearing as compared to the Contour Advance electrode (CI512).

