8.3.2 Electrode placement

Report of EA32 electrode placement as confirmed by X-ray (preferably a lateral or modified Stenver's view).

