10 DATA MANAGEMENT

Data collection is performed through electronic data capturing (EDC) on eCRFs. Site personnel will be trained on the completion of the eCRFs. Data validity has to be confirmed by the investigator through an electronic signature captured by the EDC system. Additional data is to be collected through the clinical fitting and electrophysiology software. The file records should be anonymized and then identified using the study number and the patient's study identifier (e.g. CLTD5626-MEL-01 3 month.cdx4).

Surgical experiences will be collected in written form on questionnaire but in addition the investigator may provide a video recording of the surgery in DVD or other digital format (to be uploaded to the sponsor's file server). Results from intra-operative X-rays can be summarized on the surgical questionnaire but the image or images should remain available for source verification.

An additional eCRF will be provided for summary results obtained from post-operative CT scans. However the anonymized raw image data will also be collected so that the results can be verified by the coordinating investigator and the consultant radiologist. The data should be provided in a standard DICOM format on either machine readable disk (i.e. DVDRom) or uploaded to the sponsor's file server. The file folder should be identified using the patient's study identifier (e.g. CLTD5626-MEL-01 CT scan).

Electronically captured data on e-CRFs are stored in a SQL database located on a server at Cochlear Limited.

eCRFs are reviewed by Data Management and electronic data clarification forms (eDCFs) are generated for data inconsistencies, which are sent to the investigational site. EDC has built-in edit checks and generates data clarification forms automatically. In addition, the clinical project manager (CPM) may review the data from a medical and scientific perspective and create DCFs where appropriate. Responses to eDCFs are entered in EDC.

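### Section 7 counts tip fold-over on X-ray only, so one seen only on CT can fall outside both electrode-position counts; the plan does not say whose CT reading is analysed

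*Combined protocol and SAP*

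**What the plan says.** Section 7 lists the device risks to be collected. Item 1 is "The number and percentage of subjects with electrode tip fold-overs as determined by X-ray". Item 2 is "The number and percentage of subjects with electrode not fully within the scala tympani as determined by cone beam CT scan". Each item names one modality.

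Section 8.7.7 describes the imaging. On X-ray it says "The presence of electrode tip fold-over may be detected intra-operatively". On the post-operative cone beam CT it says "The resultant scan will be assessed post-operatively by the surgical team".

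Section 10 covers recording. For X-ray: "Results from intra-operative X-rays can be summarized on the surgical questionnaire but the image or images should remain available for source verification". Section 8.7.9 has the surgeons complete that questionnaire. For CT there is a dedicated eCRF, and the anonymised raw images are collected "so that the results can be verified by the coordinating investigator and the consultant radiologist".

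The placement measure is described in two ways. Section 5.1.3.1 uses intra-operative X-ray and post-operative cone beam CT. Section 8.3.2 reads "Report of EA32 electrode placement as confirmed by X-ray" and does not mention CT.

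On symptoms, Section 4.2 says "The presence of a tip fold-over does not usually produce any clinical symptoms or adverse effect".

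**The concern.** There are two gaps. The first is in the definition. Fold-over is tied to X-ray, while CT is tied only to scalar position. The plan collects CT images of the same array but has no rule for a fold-over that appears there and not on the X-ray. Because fold-over is usually silent by the plan's own account, symptoms cannot be relied on to reveal such a case.

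The second is in the reading. The CT is assessed by the team that placed the electrode. A second reader is available, but verification is permissive. The plan gives no order of reading, no masking, no rule for disagreement and no statement of which reading is tabulated.

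Both gaps could plausibly lower the counts in an unblinded single-arm study. The counts matter for describing the device: Section 3 reports fold-over in 32% of early feasibility cases and attributes later sheath changes partly to it, and Section 4.5 builds the risk-benefit argument on correct scala tympani placement. Section 4.2 adds that a folded tip could limit speech recognition, so an unrecorded case would also make that subject's speech result harder to interpret.

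**Working it through.** The plan gives no sample-size or precision figure for these counts (Section 8.6.3: 12 subjects, no estimation), so there is no design figure to reproduce. The main check is to apply the definitions to each possible case.

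**Which count does a case enter?**

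| Imaging finding | Section 7 item 1 | Section 7 item 2 |
|---|---|---|
| Fold-over seen on X-ray | Counted | Depends on scalar position |
| Fold-over seen only on CT, array not fully in scala tympani | Not counted | Counted, but as malposition |
| Fold-over seen only on CT, array fully in scala tympani | Not counted | Not counted |
| Fold-over seen on X-ray, corrected by re-insertion | Not stated | Depends on final position |

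The third row is the gap. The fourth is a related ambiguity: Section 8.7.7 foresees correction during surgery, but Section 7 does not say whether a corrected case stays in the count.

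**Who reads what?**

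- CT: the surgical team (Section 8.7.7), with possible verification by the coordinating investigator and the consultant radiologist (Section 10).
- X-ray: no reader is named. The result can go on a form that the surgeons complete (Sections 8.7.9 and 10), which suggests a surgical reading but does not state one.
- Reading analysed: not stated for either modality.

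**Scale of one case** (n = 12, exact Clopper-Pearson 95% intervals)

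- One case: 1/12 = 8.3 percentage points.
- 0/12: upper limit 1 − 0.025^(1/12) = 26.5%, so 0 to 26.5%.
- 1/12: lower limit 1 − 0.975^(1/12) = 0.2%, upper limit 38.5%, so 0.2 to 38.5%.
- Section 3 gives temporal-bone rates of 3/110 = 2.7% for fold-over (agreeing with its stated figure of under 3%) and 3.3% for dislocation. Both lie inside both intervals.

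**How likely is a missed case?**

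- At a true rate p = 3/110, the chance of at least one fold-over in 12 is 1 − (1 − 0.0273)^12 = 28%.
- The documents do not give the sensitivity s of X-ray. Assume that s lies between 50% and 90% and that CT shows every fold-over that X-ray misses. The chance of at least one fold-over missed on X-ray is then 1 − (1 − p(1 − s))^12: 15% at s = 50%, 9% at s = 70% and 3% at s = 90%.

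**The case against.** The strongest reply is that little rests on these counts. Section 7 itself says that the fold-over data are not meant to measure treatment success. The numbered safety endpoints in Section 8.2.1 are adverse-event reports, electrode placement is an additional measure, and Section 9 sets no pass/fail criteria. Section 3 leaves the dislocation-rate question to a separate multicentre investigation. All of this stands, and it limits the weight of the point.

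A reader might also infer several things that the documents do not support.

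- **That a CT-only fold-over would go unrecorded.** It could appear on the CT eCRF (Section 10) or on an adverse-event or device-deficiency form (Section 8.7.13). It is missing from the defined number and percentage, not necessarily from the data.
- **That the count is limited to intra-operative films.** Section 7 says X-ray without a time, and Table 1 shows bracketed imaging at both surgery and activation. A later X-ray could bring a case in.
- **That the plan expressly excludes CT findings.** It does not. The omission follows from reading item 1 literally.
- **That the surgical team is the only reader, or the stated reader of both modalities.** Its role is explicit for CT only. CT image collection is firm, with verification as its stated purpose. The plan does not say who completes the CT eCRF, or whether that comes before the radiologist's look.

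These replies narrow the point. They do not supply a rule for CT-only fold-overs or name the reading to be analysed.

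**Conclusion.** The point holds as a correctable gap in outcome definition and assessment. Read literally, Section 7 omits from both counts a fold-over visible only on CT with the array inside the scala tympani. The plan assigns the CT assessment to the operating team without saying whether that reading or the radiologist's is reported. Sections 5.1.3.1 and 8.3.2 disagree on the modality for placement.

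The effect is possible under-counting. Its direction is plausible, but its amount is not shown. The 3% to 15% chance of at least one missed case rests on the assumed X-ray sensitivity, on CT finding the remainder and on the temporal-bone rate applying in patients. That rate is quoted after allowing for use errors, so it is not a like-for-like clinical benchmark.

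It is tempting to say that one case would decide whether the device meets the reference rates. It would not: the intervals for 0/12 and 1/12 both contain 2.7% and 3.3%, and 8.3 points is simply the weight of any single event among 12 subjects. Nor do the stated objectives make these counts a test of the sheath redesign. The case for change is that the reported number should mean what a reader will take it to mean, and that the resources needed are already in the plan.

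**What to change.** 1. **Section 7, item 1:** count a fold-over seen on X-ray or on cone beam CT. Report those corrected during surgery separately from those present on final imaging.
2. **Sections 8.7.7 and 10:** make the consultant radiologist's reading of the CT images already being collected the analysed value for scalar position and for CT-detected fold-over. Keep the surgical team's reading on record and report disagreements between the two.
3. **Section 8.3.2:** reconcile it with Section 5.1.3.1 and Section 7 so that all three name the same modalities for placement.

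The cost is small. The radiologist, the images and the CT eCRF are already in Section 10, and no additional imaging is requested. The optional check becomes a required reading of each available CT, at most about 12; the number may be lower because Table 1 brackets the imaging entries without explanation. The reported fold-over count may rise.

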8.7.8 Electrically evoked compound action potentials – ECAP (Surgery)

ECAP thresholds will be recorded using the AutoNRT algorithm in the CR220 Intra-operative Remote Assistant or Custom Sound EP software.

8.7.9 Surgical questionnaire

Surgeons will complete the CI532 surgical questionnaire CRF to record the usability and surgical outcomes with the CI532 cochlear implant.

8.7.10 Activation (approximately 1 month post-surgery)

The CI532 cochlear implant will be activated with a commercially available Nucleus CP910 or CP920 Sound Processor and Custom Sound programming software as for recipients of existing devices. This will take place approximately 3 – 4 weeks after surgery (plus/minus 2 weeks).

Prior to activation of the sound processor, impedances and T/C levels will be determined. These data will be extracted from anonymized computer record files (“CDX”) produced by the Custom Sound software.

Initially the default ACE sound coding strategy will be used with the parameters pulse rate 900 pps per channel, 25 µs / phase, mode MP1+2, and 8 maxima. These parameters may be adjusted afterward according to local procedures to improve subjective sound quality, if deemed necessary by the clinician. The sound processor shall be programmed with the default Nucleus 6 input processing options (SCAN). Additional custom programs can be added to the sound processor in program slots 2, 3 & 4 as required.

8.7.11 Acoustic Component Fitting (approximately 1 month post-surgery)

In the event that a subject retains aidable hearing, they will be fitted with the Nucleus 6 acoustic component (ACO). The ACO will be appropriately fit using the National Acoustics Laboratories’ hearing aid fitting strategy and assess the degree to which real-ear targets are met for each subject.

8.7.12 Device characteristics (Activation, 3 months, 6 months and 12 months post-activation)

Device characteristics will be recorded at every postoperative visit and maintained within the subject’s anonymous cdx. file (approximately one month post-surgery), at three, six and 12 months post-activation.

8.7.13 Safety

The investigator will complete an Adverse Event (AE) CRF if any AE or Adverse Device Effect (ADE), or a Device Deficiency (DD) CRF if any DD is reported or observed for a subject during the investigation, even if they were acknowledged as risk factors in the Patient Informed Consent (PIC) form.

8.8 Medical care post-investigation

Routine medical care from the implanting centre will be provided for the subjects after the clinical investigation has been completed. Subjects will be followed-up as per the centres’ standard procedures.

8.9 Monitoring Plan

The sponsor will appoint a Study Monitor to perform regular visits at the study site, as defined in the study Monitoring Plan. Prior to the first subject enrolment an initiation visit will be performed by the Clinical Project Manager or delegate and the Study Monitor ensuring that assigned study personnel are familiar with this Clinical Investigation Plan and procedures and device handling, trained in GCP compliance, electronic CRF (eCRF) completion, AE reporting, and maintenance of study related documentation.

The Study Monitor will ensure compliance with the clinical investigation plan and ISO14155, accurate data recording on the eCRFs, will raise data queries, will monitor recruitment rates and adherence to follow-up schedules. The Study Monitor will also check the upkeep of the

investigator file. The investigator shall permit and assist the Study Monitor to carry out verification of completed eCRFs against data in the source documents.

Source documents are defined as any printed, optical or electronic document containing source data (hospital records, audiograms, speech test results, laboratory notes, device accountability records, radiographs, records kept at the investigational site) containing data necessary for the reconstruction and evaluation of the clinical investigation. The extent of source data verification is defined in the Monitoring Plan. The investigator shall provide all requested documentation in a timely and organized manner.

The Study Monitor shall inform the Sponsor about any problems relating to facilities, technical equipment or medical staff at the study site. The Study Monitor shall provide the CPM with written reports, after each visit or contact with the investigational site.

The investigator has to inform the Sponsor about any additional local requirements that may impact the work of a monitor especially if access to source data may be limited by local regulations. This is to ensure any necessary action to be taken before the study start to allow proper monitoring according to the ISO Standard.

9 STATISTICAL CONSIDERATIONS

All subjects who are recruited to the clinical investigation will constitute the intention-to-treat (ITT) population for the purposes of safety evaluation. Only subjects implanted with the CI532 will be considered as the completed cases (CC) population and per protocol (PP) analysis of the primary endpoint will be performed.

Where the CC population is insufficient, the sponsor reserves the right to ask the centres to recruit additional cases in order to reach the desired sample size of 12. As this is a feasibility clinical investigation, there have been no formal power or sample size estimations performed for the primary objectives.

To understand if measurable low frequency thresholds can be maintained with implantation using the CI532 cochlear implant and fit with the acoustic component:

1. Audiometric data will be summarized at each follow-up time point to assess any changes in hearing sensitivity and to characterize the impact of the procedure on residual hearing.
2. The degree of hearing will be reported and tabulated as the number of subjects who have measurable residual hearing post CI532 implantation.

The number, severity and relationship of adverse events will be reported and tabulated. The rate of device-related adverse events will be compared to known rates of device-related adverse events for the commercially approved Nucleus cochlear implants.

Pre- to post-operative gains in speech and SSQ scores will be tested using paired comparisons (Student's t or non-parametric test if more appropriate). GBI scores will be compared to a hypothesised mean score of 0 (no benefit).

There are no pass/fail criteria to be applied to the results of the clinical investigation.

If required an interim analysis and report on three month speech and hearing threshold data will be provided for the purposes of submission to the TGA.

The characteristics of the study group will be presented descriptively. Quantitative variables such as age will be presented with mean, standard deviation, median, minimum and maximum and 95% CI. Qualitative variables such as age or gender will be presented as percentages and observed frequencies. If differences in outcome are found for subgroups defined by baseline age or gender, analyses will be performed to explore the possible role of other baseline characteristics to explain the results.

Supportive efficacy analyses will include analysis of individual data for all measures to establish the proportions of those subjects showing improvement, no change, and decrement in performance on the primary audiometry endpoint.

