8.6.4 Criteria and procedures for subject's withdrawal or discontinuation

Any subject may voluntarily discontinue the study at any time without prejudice. The Investigator may discontinue a subject from the study at any time if (s)he considers that remaining in the study compromises the subject's health or the subject is not sufficiently cooperative. In either event, reason(s) for discontinuation should be recorded on a study withdrawal form, provided as part of the CRFs for the study. Possible reasons for study discontinuation include the following:

- AE necessitating discontinuation from the study
- The subject is lost to follow-up
- Voluntary decision to withdraw consent made by the subject⁶
- Investigator decision⁷
- Other reason

In case of a subject lost-to-follow-up, the Investigator must attempt to contact the subject (or relative/family contact) by phone, email or letter at least three times. If attempts are unsuccessful, the 'subject withdrawal' form is to be completed in the study file and reported, as appropriate, in required reports to the Sponsor, EC and TGA.

During surgery, an alternative device (e.g., CI522 or CI512) may be implanted in subjects where there are substantial difficulties with the CI532. These subjects will continue the clinical investigation and their outcomes will be compared to those subjects who received the CI532 device.

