8.6.5 Subject replacement

The total number of subjects enrolled in the clinical investigation is 12. If a subject withdraws pre-operatively, they will be replaced by a newly recruited subject who meets the selection criteria for participation.

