8.6.6 Point of enrolment

Subjects are recruited to the study by the investigators usually during the course of medical consultation. Subjects will be sequentially enrolled once Cochlear Asia Pacific receives a properly executed Informed Consent form and has approved the preoperative candidacy evaluation in writing.

⁶ Withdrawal of consent is defined as the subject's voluntary decision to revoke consent to continue participation in the study.

⁷ Subject withdrawal from the study is defined as an Investigator decision. The Investigator may elect to withdraw a subject from the study at any time if he/she considers that remaining in the study compromises the patient's health or if the Investigator considers the subject lost to follow-up.

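### The safety set is all recruited subjects, so counting anyone never operated on would lower the device-related event rate that is compared with marketed implants

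*Combined protocol and SAP*

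**What the plan says.** Section 9 (Statistical Considerations) assigns one population to safety: "All subjects who are recruited to the clinical investigation will constitute the intention-to-treat (ITT) population for the purposes of safety evaluation". The efficacy set (CC/PP) is limited to subjects implanted with the CI532. Section 9 then says that the device-related event rate "will be compared to known rates of device-related adverse events for the commercially approved Nucleus cochlear implants". No treated or operated set is defined anywhere. The glossary in section 22.2 does not help, because it defines ITT by randomisation and this study has a single arm.

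On timing, section 8.6.6 says "Subjects are recruited to the study by the investigators usually during the course of medical consultation". Enrolment follows once the sponsor holds the signed consent and "has approved the preoperative candidacy evaluation in writing". Section 8.6.5 says "If a subject withdraws pre-operatively, they will be replaced by a newly recruited subject", and also "The total number of subjects enrolled in the clinical investigation is 12". If too few subjects receive the CI532, section 9 lets the sponsor "recruit additional cases in order to reach the desired sample size of 12".

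Table 1 marks adverse events from surgery onward and leaves the pre-operative cell blank. Section 8.7.13 has a general rule that any event during the investigation is recorded. On subjects given an alternative device during surgery, section 8.6.4 says "These subjects will continue the clinical investigation and their outcomes will be compared to those subjects who received the CI532 device".

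Section 7 adds a comparison of complete hearing loss with the Contour Advance electrode (CI512). Section 8.7.2.1 counts total hearing loss in the CI532-implanted population.

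**The concern.** Safety is a primary objective, and its planned form is a comparison of event frequency with an outside benchmark. Such a comparison needs a denominator of people who could have had the event. A subject recruited at consultation who withdraws before surgery has no device and no operation. That subject can add one to the denominator but nothing to the device-related numerator. Any error therefore runs one way, towards making the CI532 look safer than it was among those operated on.

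What is at stake is the accuracy of a descriptive safety figure. Section 9 sets no pass/fail criteria and section 5.2 states no formal hypothesis.

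**Working it through.** **Inputs.** The plan's own figure is 12 subjects. Section 8.6.3 says that no sample-size estimation was done, so there is no derivation to reproduce. The documents give no pre-operative withdrawal rate, expected event rate or benchmark rate. The number never operated on (k) and the number with an event (x) are therefore assumptions, shown as ranges.

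**Formula.** Let m be the subjects operated on. The rate among them is x/m and the rate in the all-recruited set is x/(m+k). The relative understatement is 1 − m/(m+k) = k/(m+k), whatever x is, provided x > 0.

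**Results for m = 12**, with exact (Clopper-Pearson) two-sided 95% intervals:

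| k | Relative understatement | x = 1 | x = 3 |
|---|---|---|---|
| 0 | 0% | 1/12 = 8.3% (0.2–38.5) | 3/12 = 25.0% (5.5–57.2) |
| 1 | 1/13 = 7.7% | 1/13 = 7.7% (0.2–36.0) | 3/13 = 23.1% (5.0–53.8) |
| 2 | 2/14 = 14.3% | 1/14 = 7.1% (0.2–33.9) | 3/14 = 21.4% (4.7–50.8) |

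With no events, the upper 95% limit falls from 26.5% (0/12) to 24.7% (0/13) or 23.2% (0/14).

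If one subject receives a back-up device and recruitment continues to 12 CI532 recipients, then m = 13. The understatement is 1/14 = 7.1% for k = 1 and 2/15 = 13.3% for k = 2.

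**How likely is k ≥ 1?** For an assumed withdrawal probability p per subject, the chance of at least one among 12 is 1 − (1−p)^12. That is 22%, 46%, 72% and 93% for p = 2%, 5%, 10% and 20%.

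**Would the CC/PP set be a better denominator?** Assume 12 CI532 recipients, three of them with an event, one back-up recipient with an event, and one pre-operative withdrawal:

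- operated: 4/13 = 30.8% (9.1–61.4)
- recruited: 4/14 = 28.6% (8.4–58.1)
- CI532-implanted only: 3/12 = 25.0% (5.5–57.2)

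In this example the all-recruited set lowers the rate by 30.8 − 28.6 = 2.2 points and the CC/PP set by 30.8 − 25.0 = 5.8 points. The CC/PP set does worse because it discards an event in a subject whose CI532 insertion was abandoned.

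**Complete hearing loss.** Section 7 names the Contour Advance as the reference. Section 8.1 describes that electrode as the comparator. Neither they nor section 9 give a rate, source, time point or baseline hearing for it. Sections 2 and 3 say that subjects are chosen for better low-frequency hearing, so whether the comparison is like for like depends on a reference group that is not described.

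**The case against.** The strongest reply is that dilution may never occur. Section 8.6.5 fixes enrolment at 12 and replaces pre-operative withdrawals. If the replacement takes over the withdrawn subject's place in the count, k = 0 and the rate is right. This stands as a reason to state the point conditionally. It does not remove it: section 8.6.5 limits the number enrolled, section 9 speaks of those recruited, section 8.6.6 treats the two as separate steps, and section 9 allows further recruitment.

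Section 9 also does not write a denominator beside the word rate. All-recruited is inferred because it is the only set assigned to safety. The blank pre-operative cell in Table 1 could suggest that safety evaluation starts at surgery, but a collection schedule does not define an analysis set.

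The effect is small, and a reader given the counts and the number never operated on could re-base the rate. That also stands.

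Three stronger readings are tempting, and the documents do not support them:

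- A reader might infer that the study rate is known to mismatch the benchmark. The source of the known rates is not identified, so a mismatch is possible but not shown.
- A reader might infer that complete hearing loss has two competing denominators, because section 7 lists it with safety. The specific rule in section 8.7.2.1 largely settles this in favour of the CI532-implanted population, and a never-operated subject has no post-operative audiogram.
- A reader might infer that the Contour Advance comparison is already shown to be unfair. Without the reference group's baseline thresholds, that cannot be judged either way.

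**Conclusion.** The concern holds as a conditional, minor point. As written, the safety set admits subjects who cannot have a device-related event, and counting them can only lower the rate compared with marketed implants. With 12 operated subjects the relative loss is 7.7% for one such subject and 14.3% for two.

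This rests on two assumptions: that at least one never-operated subject is counted, and that the rate uses the only safety population the plan defines. The shift from 25.0% to 23.1% or 21.4% is well inside the sampling error at this sample size, and it changes no formal decision. Keeping back-up recipients in the safety set is right. The missing Contour Advance reference is a separate, lesser gap in detail.

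**What to change.** For device- and procedure-related event rates, define the safety set as all subjects in whom the study operation was begun, including those who received a back-up device, with the latter also shown separately. State the moment that counts as begun. It should be early enough to keep procedure-related events before array insertion, since section 7 counts those as safety. List pre-operative withdrawals, and any events they had, apart from the rates. Do not substitute the CC/PP set. Naming the source of the known rates would let a reader check that they too are per implanted recipient.

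For complete hearing loss, use the CI532-implanted population of section 8.7.2.1 and show back-up recipients separately. Compare with Contour Advance only against a named source with similar baseline thresholds; otherwise report the study rate alone.

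The safety-set change is wording only and needs no extra data. Its downside is a slightly higher stated rate if anyone withdraws before surgery. Keeping the Contour Advance comparison would require a historical source that the documents do not identify, so that comparison may have to be dropped.
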